8.5 Instructions for the Patients

Section 4.4.4 provides diet and activity instructions for patients enrolled in the study.

Patients will be provided with instructions on daily completion of the eDiary. A practice session with a hypothetical scenario should be administered to ensure the patients' comprehension of the questions and the information to be entered. In addition, prohibited medications should be reviewed with the patients. Patients will be instructed to bring their eDiary to each clinic visit and return their investigational product (used and unused).

Patients should be instructed to take investigational product twice daily at approximately the same times each day (approximately 12 hours between doses). For dosing on Day 1 (Visit 2), the first dose is to be taken at the study site, and patients should be advised to take the second dose depending on the time of the site visit and the patient's usual routine.

Patients should use appropriate contraceptive measures for the duration of their participation in the study. (See Section 4.4.3)

8.6 Unscheduled Visits

Additional examinations and laboratory assessments may be performed as necessary to ensure the safety and well-being of the patients during the study period. Unscheduled visit eCRFs should be completed for each unscheduled visit.

8.7 Compliance with Protocol

All assessments will be conducted at the appropriate visits as outlined in [Table 1–1](#), and the timing of the visits should occur as close as possible to the day specified. At each visit, the patient will be asked if the patient changed the dose/regimen of any existing concomitant medications or initiated the use of any new concomitant medications since the last visit to ensure compliance with the protocol.

Investigational product compliance during any period will be closely monitored by counting the number of tablets dispensed and returned. Every effort will be made to collect all unused investigational product.

8.8 Early Discontinuation of Patients

A premature discontinuation will occur when a patient who signed the informed consent form (ICF) and has been randomized ceases participation in the study, regardless of circumstances, before completion of the study. Patients can be prematurely discontinued from the study for one of the following reasons:

- Adverse event (AE)
- Lack of efficacy
- Withdrawal of consent (a clear reason must be documented)
- Lost to follow-up (Every effort must be made to contact the patient; a certified/traceable letter must be sent.)
- Pregnancy
- Protocol violation
- Non-compliance with study drug
- Study terminated by Sponsor
- Site terminated by Sponsor
- Other

Patients may voluntarily withdraw from the study at any time. Notification of early patient discontinuation from the study and the reason for discontinuation will be clearly documented on the appropriate case report form. All randomized patients who prematurely discontinue from the study, regardless of cause, should be seen for final study assessments. The final assessments will be defined as completion of the evaluations scheduled for Visit 7/Early Termination and Visit 8 Safety Follow-up, 4 weeks post the last dose of IP.

8.9 Withdrawal Criteria

Women who become pregnant (Section 9.4) and patients who meet investigational product discontinuation criteria related to abnormal liver function tests (Section 9.5) and advised not to be re-challenged will be withdrawn from the study and should refrain from taking investigational product. The patient should return to the clinic for early termination procedures (Visit 7) and the Safety Follow-up Visit 8. Patients who reply with “yes” to questions 4 or 5 in the suicidal ideation section or “yes” to any question in the suicidal behavior section of the C-SSRS at Visits 3 through 6 must be withdrawn from the study and should receive appropriate follow-up as in routine clinical practice, including the Early Termination Visit 7 and the Safety Follow-Up Visit 8.

A patient with a condition and/or a situation that, in the investigator's opinion, may put the patient at significant risk, may confound the study results, or may interfere significantly with the patient's participation in the study may be withdrawn from treatment.

8.10 Withdrawal from Future Biomedical Research

A patient who initially consents can withdraw that consent at any time and have his or her sample destroyed, including any by-products of the sample whenever possible. If a patient withdraws consent, their physical sample will be destroyed and no new health information identifying the patient will be gathered after that date. However, once the genetic data is anonymized and placed into the biorepository database after study database lock, the information cannot be withdrawn.

8.11 Study Termination

The study may be stopped at his/her study site at any time by the site investigator. Allergan may stop the study (and/or the study site) for any reason, with appropriate notification.

9. Adverse Events

AEs occurring during the study will be recorded on an AE case report form. If AEs occur, the first concern will be the safety of the study participants.

9.1 Definitions

9.1.1 Adverse Event

An AE is any untoward medical occurrence in a patient or clinical investigation patient administered a pharmaceutical product and that does not necessarily have a causal relationship with this treatment. An AE can therefore be any unfavorable and unintended sign (including an abnormal laboratory finding), symptom, or disease temporally associated with the use of a medicinal (investigational) product, whether or not related to the medicinal (investigational) product. In addition, during the screening period, AEs will be assessed regardless of the administration of a pharmaceutical product.

Note: AEs must be collected once informed consent has been obtained, regardless of whether or not the patient has been administered study drug.

Progression of treatment indication including new or worsening of anticipated clinical signs or symptoms, which are collected as clinical efficacy variables and assessed as unequivocally associated with the disease progression and /or lack of efficacy, should NOT be reported as AEs unless the disease progression is greater than anticipated in the natural course of the disease.

AEs will be assessed, documented, and recorded in the eCRF throughout the study (ie, after informed consent has been obtained). At each visit, the investigator will begin by querying for AEs by asking each patient a general, non-directed question such as “How have you been feeling since the last visit?” Directed questioning and examination will then be done as appropriate. All reported AEs will be documented on the appropriate case report form.

9.1.2 Serious Adverse Event

An SAE is any AE occurring at any dose that results in any of the following outcomes: death, a life-threatening AE, inpatient hospitalization or prolongation of existing hospitalization, a persistent or significant disability/incapacity, or a congenital anomaly/birth defect. Important medical events that may not result in death, be life-threatening, or require hospitalization may be considered a SAE when, based upon appropriate medical judgment, they may jeopardize the patient and may require medical or surgical intervention to prevent one of the outcomes listed in this definition. (See Section 9.3 for procedures for reporting an SAE.)

Allergan considers all cancer adverse events as SAEs. In addition, Allergan considers any abortion (spontaneous or nonspontaneous) as an SAE.

Pre-planned surgeries or procedures for pre-existing, known medical conditions for which a patient requires hospitalization is not reportable as an SAE.

Any pre-planned surgery or procedure should be clearly documented in the site source documents by the medically qualified investigator at the time of the patient's entry into the study. If it has not been documented at the time of the patient's entry into the study, then it should be documented as a SAE and reported to Allergan.

9.1.3 Severity

A clinical determination will be made of the intensity of an AE. The severity assessment for a clinical AE must be completed using the following definitions as guidelines:

Mild	Awareness of sign or symptom, but easily tolerated.
Moderate	Discomfort enough to cause interference with usual activity.
Severe	Incapacitating with inability to work or do usual activity.

9.1.4 Relationship to Study Drug or Study Procedure

A determination will be made of the relationship (if any) between an AE and the study drug or study procedure, as applicable. A causal relationship is present if a determination is made that there is a reasonable possibility that the AE may have been caused by the drug or study procedure.

9.2 Procedures for Reporting Adverse Events

Any adverse event must be recorded on the appropriate case report form.

All SAEs that are drug-related and unexpected (not listed as treatment-related in the current Investigator's Brochure) must be reported to the governing Institutional Review Board/Independent Ethics Committee (IRB/IEC) as required by the IRB/IEC, local regulations, and the governing health authorities. Any adverse event that is marked 'ongoing' at the exit visit must be followed-up as appropriate.

9.3 Procedures for Reporting a Serious Adverse Event

Any SAE occurring during the study period (beginning with informed consent) and for at least 30 days after the last dose of study drug must be immediately reported but no later than 24 hours after learning of an SAE. SAEs must be reported to Allergan (or Agent of Allergan)

as listed on the Allergan Study Contacts Page and recorded on the SAE form. All patients with an SAE must be followed up and the outcomes reported. The investigator must supply the sponsor and the IRB/IEC with any additional requested information (eg, autopsy reports and discharge summaries).

In the event of an SAE, the investigator must:

1. Notify Allergan immediately by fax or email using the SAE form (contact details can be found on page 1 of the SAE form); phone numbers and relevant Allergan personnel contacts are also on the front page of protocol and Study Contacts Page.
2. Obtain and maintain in his/her files all pertinent medical records, information, and medical judgments from colleagues who assisted in the treatment and follow-up of the patient.
3. Provide Allergan with a complete, written description of the adverse event(s) on the SAE form describing the event chronologically, including any treatment given (eg, medications administered, procedures performed) for the adverse event(s).
Summarize relevant clinical information about the event: signs, symptoms, diagnosis, clinical course and relevant clinical laboratory tests, etc. Include any additional or alternative explanation(s) for the causality which includes a statement as to whether the event was or was not related to the use of the investigational drug.
4. Promptly inform the governing IRB/IEC of the SAE as required by the IRB/IEC, local regulations, and the governing health authorities.

9.4 Exposure to Investigational Product during Pregnancy

Study center personnel must report every pregnancy from the time he or she signs the ICF for the trial until 30 days after the last dose of investigational product on the Pregnancy Form as soon as possible (within 24 hours of learning of the pregnancy to **the SAE/pregnancy fax number, [REDACTED]**) even if no AE has occurred. Pregnancies in female partners of male patients must also be reported. The pregnancy must be followed to term and the outcome reported by completing a follow-up Pregnancy Form. If, however, the pregnancy is associated with a SAE (eg, if the mother is hospitalized for hemorrhage), in addition to the Pregnancy Form, a separate SAE Form must be filed as described in Section 9.3 with the appropriate serious criterion (eg, hospitalization) indicated.

9.5 ALT or AST Elevations

A post treatment event of ALT or AST $\geq 3 \times \text{ULN}$ is considered an Event of Clinical Interest. Any patient with this laboratory result after investigational product was taken must have repeat testing within 48 to 72 hours to confirm the abnormality. For this repeat testing, the following labs must be drawn: hematology and chemistry panels, international normalized ratio (INR), and a toxicology screen for acetaminophen. In addition, the investigator will perform a complete history and exam to evaluate for possible liver disease.

All Events of Clinical Interest must be reported to Allergan using the AE of Interest form and submitted within 24 hours of the time the Investigator becomes aware of the event. All new elements of history, physical exam, diagnostic testing results, and other relevant medical reports are to be reported for each event.

If an ALT or AST elevation $\geq 3 \times \text{ULN}$ is confirmed and the patient meets any of the following criteria, close medical follow-up is required:

- Patients with ALT or AST $\geq 3 \times \text{ULN}$ and $\leq 5 \times \text{ULN}$ and who are asymptomatic with regard to possible liver disease (ie. No fatigue, nausea, vomiting, right upper quadrant pain or tenderness, fever, rash or eosinophilia ($> 5\%$))
- Patients with ALT or AST $\geq 3 \times \text{ULN}$ and $\leq 5 \times \text{ULN}$ and (total bilirubin $< 2 \times \text{ULN}$ and INR < 1.5)

Patients who meet these criteria must be followed clinically and further medical evaluation will be done per the judgment of the investigator and in conjunction with medical personnel at Allergan. The Chemistry panel will be repeated 1 to 2 times per week to follow the course of ALT/AST elevation. An extra blood serology sample must be collected and sent to the central laboratory for further diagnostic testing at a later date if needed.

If an ALT or AST elevation $\geq 3 \times \text{ULN}$ is confirmed and the patient meets any of the following criteria, close medical follow-up is also required:

- ALT or AST $\geq 3 \times \text{ULN}$ and the patient is symptomatic with the appearance of fatigue, nausea, vomiting, right upper quadrant pain or tenderness, fever, rash, or eosinophilia ($> 5\%$)
- ALT or AST $\geq 3 \times \text{ULN}$ **and** (total bilirubin $> 2 \times \text{ULN}$ or INR > 1.5)
- ALT or AST $\geq 5 \times \text{ULN}$

For these patients, possible etiologies for acute hepatic injury must be excluded. The following laboratory tests must be performed: anti-hepatitis A IgM, hepatitis B surface

antigen, anti-hepatitis B core IgM, hepatitis C antibody, hepatitis C quantitative RNA by PCR, anti-hepatitis E IgM. An extra serology blood sample will be collected and sent to the central laboratory for further diagnostic testing at a later date if needed. The patient must be followed clinically and further medical evaluation should be done per the judgment of the investigator and in conjunction with medical personnel at Allergan. In general, the Chemistry panel should be repeated 1 to 2 times per week to follow the course of ALT/AST elevation. For procedural details on the medical evaluation of liver disease, please see the Study Reference Manual.

The investigator must contact the Allergan Medical Monitor to discuss all cases of confirmed ALT/AST elevation $\geq 3 \times$ ULN. All ALT/AST elevations must be followed until ALT and AST return to $< 1.5 \times$ ULN and there is full clinical resolution

Investigational product must be discontinued if any of the following criteria are met:

- ALT or AST $\geq 3 \times$ ULN and the patient is symptomatic with the appearance of fatigue, nausea, vomiting, right upper quadrant pain or tenderness, fever, rash, or eosinophilia ($> 5\%$)
- ALT or AST $\geq 3 \times$ ULN and (total bilirubin $> 2 \times$ ULN or INR > 1.5)
- ALT or AST $\geq 5 \times$ ULN for more than 2 weeks
- ALT or AST $\geq 8 \times$ ULN

The patient may be re-challenged with investigational product only after consultation with the Allergan Medical Monitor. For patients who are not re-challenged with investigational product, the patient should be discontinued from the study and complete the Early Termination Visit 7 and Safety Follow-Up Visit 8. Patients should receive appropriate follow-up as per standard of care.

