6.4.2 Events of Clinical Interest

Selected non-serious and serious events are of clinical interest and will require immediate reporting, recording and follow-up. The following events will be closely monitored:

- Suicidal ideations with intent, with or without a plan, (ie, Type 4 or 5 on the C-SSRS) or any suicidal behaviors
- Elevated ALT or AST lab value that is $\geq 3 \times$ the ULN
- Potential Hy's law cases: elevated ALT or AST lab value that is $\geq 3 \times$ the ULN and an elevated total bilirubin lab value that is $\geq 2 \times$ the ULN and, at the same time, an alkaline phosphatase lab value that is $< 2 \times$ the ULN.

Reporting requirements for ALT or AST elevations and potential Hy's law cases are outlined in Sections 9.5 and 9.5.1. Responses to the C-SSRS that meet the above criterion will be captured in the eTablet and monitored by Allergan. Events that are determined to be AEs or SAEs must be reported appropriately via the designated eCRF pages and forms.

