9.5.1 Potential Hy's Law Cases

Sites must report every patient who meets the following potential Hy's law criteria if this occurs within the time the patient signs the ICF until 30 days after the last dose of investigational product:

- ALT or AST $\geq 3 \times$ ULN **AND**
- Total bilirubin $\geq 2 \times$ ULN **AND**
- Alkaline phosphatase $< 2 \times$ ULN

A laboratory alert for potential Hy's laws cases will be in place, and the investigators and Allergan will be notified immediately when the above criteria have been met. Any potential Hy's laws case should be considered an SAE and also reported as an AE of Special Interest. Complete both an SAE and AE of Special Interest Form as soon as possible (within 24 hours of learning of the potential Hy's law) and fax it to the SAE fax number. The eCRF pages associated with potential Hy's law cases must be completed within 7 calendar days. Every effort to determine the cause of the liver abnormalities must be made, and close monitoring should be initiated in conjunction with the Allergan medical monitor and in accordance with the FDA "Guidance for Industry: Drug Induced Liver Injury - Pre-Marketing Clinical Evaluation" July 2009. For specific instructions, please refer to the Study Reference Manual.

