# 6.5.2.2 Hepatic Laboratory Abnormalities

The following laboratory parameters will be summarized:

Table 6–8	Criteria for Hepatic Laboratory	Abnormalities
Table 0-0	Cinteria for frepatic Laboratory	ADIIOI IIIantie

Laboratory Parameter	Categories
	$\geq 1 \times ULN$
	$\geq 1.5 \times \text{ULN}$
	$\geq 2 \times ULN$
ALT	$\geq$ 3 × ULN
	$\geq$ 5 × ULN
	$\geq$ 10 × ULN
	$\geq$ 20 × ULN
	$\geq 1 \times ULN$
	$\geq 1.5 \times \text{ULN}$
	$\geq 2 \times ULN$
AST	$\geq$ 3 × ULN
	$\geq$ 5 × ULN
	$\geq$ 10 × ULN
	$\geq$ 20 × ULN
	$\geq 1 \times ULN$
	$\geq 1.5 \times ULN$
	$\geq 2 \times ULN$
ALT or AST	$\geq$ 3 × ULN
	$\geq$ 5 × ULN
	$\geq 10 \times ULN$
	$\geq$ 20 × ULN
	$\geq 1 \times ULN$
	$\geq 1.5 \times ULN$
	$\geq 2 \times ULN$
Bilirubin Total	$\geq$ 3 × ULN
	$\geq$ 5 × ULN
	$\geq$ 10 × ULN
	$\geq$ 20 × ULN

Laboratory Parameter	Categories		
	$\geq 1 \times ULN$		
	$\geq$ 1.5 × ULN		
	$\geq$ 2 × ULN		
Alkaline Phosphatase	$\geq$ 3 × ULN		
	$\geq$ 5 × ULN		
	$\geq 10 \times \text{ULN}$		
	$\geq$ 20 × ULN		
	ALT or AST $\geq 3 \times$ ULN AND Bilirubin Total $\geq 1.5 \times$ ULN		
Concurrent Elevations.	ALT or AST $\geq 3 \times$ ULN AND Bilirubin Total $\geq 2 \times$ ULN		
Potential Hy's Law ¹	ALT or AST $\ge$ 3 × ULN AND Bilirubin Total $\ge$ 2 × ULN AND ALP < 2 × ULN		

ALT = alanine aminotransferase; AST = aspartate aminotransferase; TBL = total bilirubin; ALP = alkaline phosphatase; ULN = upper limit of normal (value provided by the laboratory).

¹ Elevations are from the same day

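### Protocol Section 9.5 requires stopping drug and a hepatitis panel only above 2×ULN bilirubin, while potential Hy's law starts at exactly 2×ULN, so a Hy's law SAE at the boundary can have no mandatory stop

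*Protocol*

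**What the plan says.** Section 9.5 of the protocol has two lists that turn on bilirubin. The upper follow-up tier, which makes a named hepatitis panel mandatory, includes ALT or AST ≥ 3×ULN with "total bilirubin $> 2 \times \text{ULN}$ or INR > 1.5". The list of criteria for which study drug must be discontinued repeats this: ALT or AST ≥ 3×ULN "and (total bilirubin $> 2 \times$ ULN or INR > 1.5". The other stopping criteria are ALT or AST ≥ 3×ULN with symptoms (or rash, fever or eosinophilia), ≥ 5×ULN for more than 2 weeks, and ≥ 8×ULN.

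Potential Hy's law is defined with the inclusive sign throughout. Section 9.5.1 requires "Total bilirubin $\geq 2 \times$ ULN" together with ALT or AST ≥ 3×ULN and ALP < 2×ULN, and treats such a case as an SAE. Section 6.4.2 has "an elevated total bilirubin lab value that is $\geq 2 \times$ the ULN". SAP Section 6.5.2.2 (Table 6–8) has "Bilirubin Total $\ge$ 2 × ULN AND ALP < 2 × ULN".

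Apart from reporting, Section 9.5.1 asks for a search for the cause and for close monitoring. Its text does not tell the site to stop the drug.

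**The concern.** The dosing rule and the SAE definition describe the same laboratory pattern but disagree at one value. A site can receive a Hy's law alert, turn to Section 9.5 for instructions, and find that nothing there requires the drug to be stopped. Section 8.9 does not fill the gap, because its compulsory liver-related withdrawal depends on meeting the Section 9.5 discontinuation criteria.

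Liver injury is the class risk the protocol itself names: Section 1.2 says ALT increases with telcagepant ended development of the earlier oral CGRP antagonists. Nothing in either document explains why exactly 2.0×ULN should count as a serious event yet fall outside the stopping rule.

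**Working it through.** No power or alpha figure is involved, so the check is of the rules themselves. First, the bilirubin thresholds side by side:

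| Place | Purpose | Total bilirubin |
|---|---|---|
| Protocol 6.4.2 | Event of clinical interest | ≥ 2×ULN |
| Protocol 9.5.1 | Hy's law SAE and laboratory alert | ≥ 2×ULN |
| SAP Table 6–8 | Hy's law summary | ≥ 2×ULN |
| Protocol 9.5, upper tier | Mandatory hepatitis panel | > 2×ULN |
| Protocol 9.5, stopping list | Mandatory discontinuation | > 2×ULN |

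The inclusive sign appears three times and the strict sign twice, each set consistent in its own use, so a text-extraction error is unlikely. All five are current text.

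**One patient.** Take ALT 4×ULN, bilirubin 2.0×ULN, ALP 1×ULN, INR 1.0, no symptoms.

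- Hy's law: 4 ≥ 3, 2.0 ≥ 2 and 1 < 2, so all three criteria are met.
- Stopping list: no symptoms; 2.0 is not > 2 and 1.0 is not > 1.5; 4 is below 5; 4 is below 8. None is met.
- Upper tier: not met, so the panel is not triggered. The patient falls in the lower tier, through its bullet for asymptomatic patients at 3 to 5×ULN.

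**All combinations on a grid.** The inputs are ALT 3.0 to 10.0×ULN in steps of 0.1 (71 values), bilirubin 1.0 to 4.0×ULN in steps of 0.1 (31), INR 1.0, 1.4, 1.5 or 1.6 (4), symptoms yes or no (2), and more than 2 weeks' duration yes or no (2), with ALP < 2×ULN. The duration flag acts only when ALT is at least 5×ULN.

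- Total: 71 × 31 × 4 × 2 × 2 = 35,216.
- Potential Hy's law (21 bilirubin values from 2.0 up): 71 × 21 × 16 = 23,856.
- Hy's law with no mandatory stop: bilirubin must be exactly 2.0, symptoms absent and INR one of the 3 values ≤ 1.5. ALT runs from 3.0 to 7.9 (50 values) without the duration flag and from 3.0 to 4.9 (20 values) with it. (50 + 20) × 3 = 210.
- Of these, no hepatitis panel either (ALT 3.0 to 4.9, either duration): 20 × 2 × 3 = 120.
- With ≥ 2×ULN in Section 9.5, both counts fall to 0.

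A second, coarser grid that also varied ALP gave the same pattern. Of 864 Hy's law combinations, 60 had no mandatory stop and 36 no panel, all at bilirubin exactly 2.0×ULN. Both counts were 0 after the change.

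These counts describe the rules, not expected patients. No combination on the first grid is left without a follow-up tier under the current text, so the INR and 5×ULN boundaries need no change.

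**Can the boundary value occur?** The documents give neither the bilirubin ULN nor the reporting precision. Assuming 0.1 mg/dL steps and a ULN of 1.0 to 1.2 mg/dL, 2×ULN is 2.0 to 2.4 mg/dL, a reportable result. It is 1 of 21 to 1 of 25 values between 2 and 4×ULN. Assuming whole µmol/L and a ULN of 17 to 21, it is 1 of 35 to 1 of 43. These are shares of possible readings; they say only that the value can arise.

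**The case against.** The best counter-argument is that the two thresholds do different jobs. Section 9.5.1 is a reporting net that runs from consent to 30 days after the last dose; Section 9.5 governs dosing. A reporting trigger slightly wider than a stopping trigger is not in itself an error, and the protocol never says that every potential Hy's law case must stop drug.

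The safeguards are also substantial. The laboratory alert is immediate. For Hy's law cases, "Every effort to determine the cause of the liver abnormalities must be made". At ≥ 3×ULN, "The investigator must contact the Allergan Medical Monitor to discuss all cases of confirmed ALT/AST elevation". Section 9.5 also requires repeat testing within 48 to 72 hours (including INR and an acetaminophen screen), a full history and examination, chemistry 1 to 2 times a week, and an extra serology sample. Section 3.6 provides blinded adjudication, and Section 3.5 gives the DSMB unblinded safety data. Under Section 8.9 a patient at significant risk "may be withdrawn from treatment". Any reportable rise in bilirubin above 2.0×ULN triggers the stop. Finally, Sections 9.5 and 9.5.1 refer to a Study Reference Manual, which may contain further instructions.

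Most of this stands as a limit on importance. The cause search may well lead to hepatitis testing in practice, so the panel gap matters less than the stopping gap. But none of these safeguards requires the drug to be stopped, and a mandatory stopping rule should be complete in the protocol rather than rely on a manual. The different-purposes argument would carry weight if the lists differed by design; a difference of one boundary point, with no stated reason, looks like an oversight.

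**Conclusion.** The mismatch is real and wrong as written, but minor. It affects patients with bilirubin exactly 2.0×ULN, ALP < 2×ULN, INR ≤ 1.5, no listed symptoms and ALT or AST from 3 to below 8×ULN, provided that any level of 5×ULN or more has not itself lasted over 2 weeks. In that group stopping is a matter of judgment. From 3 to below 5×ULN the named hepatitis panel is not automatic either. At any bilirubin above 2.0×ULN, every potential Hy's law case meets both the stopping and the panel criteria.

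Very few patients can be expected at this value; the documents do not allow a rate to be estimated. The conclusion rests on the protocol and SAP text alone, without the Study Reference Manual.

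**What to change.** In Section 9.5, change the bilirubin condition from > 2×ULN to ≥ 2×ULN in both the upper follow-up tier and the stopping list. Alternatively, add to both lists a criterion that the patient meets the potential Hy's law definition in Section 9.5.1. The second option would keep the lists aligned if the definition were later revised. Leave the INR and 5×ULN boundaries alone.

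The change needs a protocol amendment with the IRB/IEC review that Section 10.2 requires, across about 75 sites. It adds no procedures, visits or patients, and the laboratory alert already uses ≥ 2×ULN. The clinical cost is that, very rarely, one more patient stops drug at exactly 2.0×ULN. Section 9.5 still allows re-challenge after consultation with the Medical Monitor.
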